Record dose of ESA and IV iron	X		Record on an ongoing basis						X		
Record number of missed dialysis visits and reason(s)			Record on an ongoing basis								
IV administration of study drug			Record on an ongoing basis								
Inflammatory biomarker samples ^o			X						X		
Adverse event monitoring	X	X	Record on an ongoing basis						X	X	
Concomitant medications (including antipruritic medications) ^p			X	Record on an ongoing basis						X	X
Structured Safety Evaluation ^f		X		X			X			X	

DP = Discontinuation Period; ESA = erythropoiesis-stimulating agent; F = Friday; IV = intravenous; M = Monday; NRS = numerical rating scale; OOWS = Objective Opiate Withdrawal Scale; PRO = patient-reported outcome; Sa = Saturday; ShOWS = Short Opiate Withdrawal Scale; Th = Thursday; Tu = Tuesday; W = Wednesday

-
- a. Each visit during the Double-blind Treatment Period will coincide with the patient's normal dialysis treatments.
 - b. The End-of-Treatment Visit in the Double-blind Phase will be the first dialysis visit following the last dose of study drug (ie, first dialysis on Week 13 [Day 85]), which also corresponds to Day 1 of the Discontinuation Period (DP Day 1).
 - c. Medical history will be updated on Day 1 with any changes since the Screening Visit, and inclusion/exclusion criteria will be confirmed prior to randomization. Antipruritic medication will be updated at each dialysis visit during the Run-in Period.
 - d. Electrocardiogram must be performed prior to the start of dialysis at screening, Day 85 (End of Treatment), or at Early Termination visit.
 - e. Pre-dialysis vital signs, including body temperature, heart rate, and blood pressure, will be recorded on Days 1, 15, 29, 43, 57, 71 and 85 (End of Treatment), or at Early Termination visit only when the patient is in a sitting or semi-recumbent position. Heart rate will be measured at each dialysis; if heart rate is clinically significant and outside the prespecified visits per Schedule of Events, the heart rate will be recorded on the relevant CRF page.
 - f. Pre-dialysis vital signs, including body temperature, heart rate, and blood pressure, will be recorded at each dialysis visit during the Discontinuation Period. Heart rate will be measured at each dialysis.
 - g. Blood samples for clinical laboratory evaluation will be taken at screening, and on Days 1 and 85 (End of Treatment), or at Early Termination visit only.

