8.9.4 Discontinuation Period Additional Assessments

Baseline ShOWS and OOWS will be the scores collected on the dialysis day on Day 85 (Double-blind EOT/Early Termination) (Table 2). Only patients who have a baseline ShOWS and OOWS will be included in the analysis.

Summary statistics for the daily ShOWs and the OOWS collected at each dialysis visit, including number of non-missing observations, mean, standard deviation, median, minimum, and maximum median of ShOWS and OOWS will be tabulated by treatment group. Figures for the overall mean scores over time will also be presented.

The ShOWS scores on discontinuation days 1, 2, 3, and >3 will be analyzed to compare the treatment groups at each visit, using an Analysis of Covariance (ANCOVA) model, with treatment group and baseline value as a covariate. The OOWS scores will be analyzed using a similar ANCOVA model at each day of collection. In addition, between-treatment group comparisons over the overall 2-Week Discontinuation Period will be performed using an MMRM with treatment group, discontinuation day, and treatment group-by-day interaction as fixed effects, baseline value as the covariate, and patient as a random effect. An unstructured covariance matrix will be used to model the covariance of within-patient scores. These analyses will be performed based on all postbaseline scores using only the observed cases without imputation of missing values.

Exploratory analyses may be performed, depending on sample size, for the subgroup of patients who also stop taking concomitant opioid medications during the 2-week Discontinuation Period.

Adverse events (AEs) and vital signs potentially related to withdrawal that occur during the 2-week Discontinuation Period will be identified based on a blinded review of the data, and will be summarized by randomized treatment group, and compared to the 2-week period prior to discontinuation.

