Day 1 of the Double-blind Treatment Period will be defined as the day of administration of the first dose of study drug and will occur on the first dialysis session day of the first treatment week (i.e., Monday for subjects on a Monday-Wednesday-Friday dialysis schedule, or Tuesday for subjects on a Tuesday-Thursday-Saturday dialysis schedule). Subjects will be administered CR845 or matched placebo as an IV bolus after the end of each dialysis session during the 12-week Double-Blind Treatment Period. Each subject is to receive CR845 or placebo 3 times weekly for a total of up to 36 doses.

During the Double-blind Treatment Period, subjects will continue to report their daily Worst Itching Intensity NRS score over the previous 24 hours. In addition, during selected study visits (see Appendix [16.1](#)), they will complete other PRO measures [Skindex-10 Scale, 5-D Itch Scale, and Patient Global Impression of Change (PGIC)]. Subjects will be instructed to record PRO measurements, including Worst Itching Intensity NRS scores, at a similar time of day, whether in the dialysis unit (on dialysis days) or at home (on non-dialysis days).

Blood samples for clinical laboratory tests will be collected at Screening and on Days 1 and 85. Blood samples for biomarkers will be collected on Days 1 and 85. Electrocardiograms (ECGs) will be monitored at the Screening Visit and Day 85. Vital signs will be monitored periodically, and adverse events and concomitant medications will be continuously recorded starting at the screening visit until the end of the Discontinuation Period or Early Termination Visit. Use of antipruritic medications, iron, and erythropoiesis stimulating agents (ESAs) and any missed dialysis sessions will be recorded throughout the Double-blind Treatment Period.

The Double-blind Treatment Period will be followed by a 2-week Discontinuation Period, during which no study drug will be administered. Subjects will be monitored and

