- TEAEs leading to study discontinuation by SOC and preferred term
- TEAEs potentially related to withdrawal by preferred term – see definition below (for Double-blind Discontinuation Population and Double-blind Discontinuation Safety Population)

Adverse events potentially related to withdrawal that occur during the 2-week Discontinuation Period will be identified based on a blinded review of the data using published criteria [[American Psychiatric Association 2013](#)]. First, subjects that have 3 or more AEs occurring within 6 days (which will include 3 dialysis visits) of the last dose of double-blind study drug from the list below programmatically will be selected for review:

1. Dysphoric mood
2. Nausea and/or vomiting
3. Muscle aches
4. Lacrimation and/or rhinorrhea
5. Pupillary dilation, piloerection, and/or sweating
6. Diarrhea
7. Yawning
8. Fever
9. Insomnia

The data for patients that have AEs potentially related to withdrawal (based on the above criteria) will be reviewed in a blinded fashion. Cases categorized as possibly related to withdrawal will be flagged and separate summaries will be produced for the Discontinuation Period and the Discontinuation Period Safety populations.

In addition, all adverse events will be listed in chronological order including subject identifier, age, race, gender, and all related event status information (start and stop dates, whether the event was ongoing, study day of onset, severity, seriousness, relationship to study drug, action taken with study treatment, and outcome). Note: For the all adverse event listing only, any screen failure subject who has an adverse event after signing ICF

will be included for completeness. Separate listings will be generated for serious adverse events (SAEs), deaths, and adverse events leading to treatment discontinuation. Additionally, a coding list of preferred terms and the verbatim text associated with them will be produced.

The incidence of TEAEs in each CMQ category (see Section [16.2](#)) will be summarized. If a subject experienced more than 1 episode of an adverse event, the subject is counted once for that preferred term; the total number of subjects reporting an event in the category will also be reported.

No statistical tests will be performed on adverse events.

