10.5 ShOWS and OOWS

Short Opiate Withdrawal Scale

SOWS-Gossop (or ShOWS) is a self-administered scale for grading opioid withdrawal symptoms over a 24-hour period. This subject-rated scale consists of 10 items, scored from 0 (none) to 3 (severe); the total score is calculated as the sum of the individual items (total score range 0–30). If any individual values are missing, the total will be missing. The higher the score, the greater the severity of associated withdrawal.

The ShOWS will be presented as a paper worksheet to be filled by each subject, at home on non-dialysis days and at the dialysis unit on dialysis days, at a similar time of the day for a given subject during the 2-week Discontinuation Period (during which no study drug will be administered).

Objective Opiate Withdrawal Scale

The OOWS-Handelsman contains 13 physically observable signs, rated present (score of 1) or absent (score of 0); the total score is calculated as the sum of the individual items (total score range 0–13), based on a timed period of 5 to 10 minutes of observation of the subjects by a rater. If any individual values are missing, the total will be missing. Higher total scores will indicate more severe withdrawal signs. The rater will be a qualified staff member who will be trained by the Sponsor.

The OOWS will be presented as a paper worksheet to be filled by a qualified staff member at the dialysis unit on dialysis days (Discontinuation days 1,3,5,8,10 and 12), at similar time of the day for a given subject during the 2-week Discontinuation Period (during which no study drug will be administered).

Analyses

Summary statistics for the daily ShOWs and the OOWS collected at each dialysis visit, including number of non-missing observations, mean, standard deviation, median, minimum, and maximum of ShOWs and OOWS, will be tabulated by treatment group for the Double-blind Discontinuation Safety Population and Double-blind Discontinuation Population. Figures for the overall mean scores over time will also be presented. The ShOWS scores on Discontinuation Period Days 2, 3, 4, 5, 6, and average assessment on days after Day 6 will be analyzed to compare the treatment groups at each visit, using an ANCOVA model, with treatment group and baseline (Day 85) value as a covariate.

[figure not shown]

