The OOWS scores will be analyzed using a similar ANCOVA model at each day of collection (Discontinuation days 1,3,5,8,10 and 12). Summary statistics will be reported for all collection time points and the average of the days after Day 6 (that is, Days 8, 10 and 12); the ANCOVA model will only be performed for the visits described above.

Additionally, OOWS will be summarized by the number and percentage of subjects who have a score = 2; number and percentage of subjects who have a score = 3; number and percent of subjects who have a score = 4; and the number and percentage of subjects who have a score >4. This will be reported by day up to Discontinuation Period Day 5, and then using the maximum any time during Days 8 to 12; and then the maximum anytime during the Discontinuation Period.

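### On the regular dialysis schedule, the 6 days after the last double-blind dose hold two dialysis visits, not the three stated in SAP 9.2; the withdrawal screen's window and anchor need reconciling

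*SAP*

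**What the plan says.** SAP 9.2 sets out how possible withdrawal cases are found. Its scope is "Adverse events potentially related to withdrawal that occur during the 2-week Discontinuation Period". The first step is programmed: a subject goes forward if he or she has "3 or more AEs occurring within 6 days (which will include 3 dialysis visits) of the last dose of double-blind study drug", taken from nine listed symptom groups. Those subjects are then reviewed blind, and cases judged possibly related to withdrawal are flagged and summarised.

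The calendar is given elsewhere:

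- SAP 2.2.1 places Day 1 on "Monday for subjects on a Monday-Wednesday-Friday dialysis schedule, or Tuesday for subjects on a Tuesday-Thursday-Saturday dialysis schedule", with study drug given "3 times weekly for a total of up to 36 doses". The dosing visits in the Schedule of Events end on Day 82.
- Footnote b to the schedule in Protocol 6.5.1 puts the End-of-Treatment Visit at the "first dialysis visit following the last dose of study drug (ie, first dialysis on Week 13 [Day 85"; that day is also Discontinuation Period (DP) Day 1.
- SAP 10.5 places the observer-rated withdrawal scale on "dialysis days (Discontinuation days 1,3,5,8,10 and 12", and separately summarises "the average of the days after Day 6 (that is, Days 8, 10 and 12".

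Protocol 8.9.4 says that adverse events and "vital signs potentially related to withdrawal that occur during the 2-week Discontinuation Period will be identified" by a blinded review. It gives no event count and no day window.

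**The concern.** The text in brackets reads as the reason for choosing 6 days: the window is meant to span three dialysis visits. If 6 days hold only two, either the length or the starting point is wrong, and the text does not say which. The rule is a threshold that decides who is reviewed at all. A subject with two listed events by Day 88 and a third with onset on Day 89 would not be selected, although Day 89 is the third dialysis visit after the last dose. Assessing possible physical dependence is the purpose of the Discontinuation Period, so the selection rule should be one that two programmers would code the same way.

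**Working it through.** **Inputs.** Regular sessions fall on Days 1, 3 and 5 of each 7-day week, so the gaps between sessions are 2, 2 and 3 days (sum 7). The last planned dose is on Day 82. DP Day d is study Day 84 + d, so DP Days 1, 3, 5, 8, 10 and 12 are study Days 85, 87, 89, 92, 94 and 96.

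**Step 1: try to reproduce the stated three visits.** Offset = visit day − last-dose day. After Day 82 the offsets are:

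- 85 − 82 = 3
- 87 − 82 = 5
- 89 − 82 = 7

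Offsets 1 to 6 contain two visits, and offsets 1 to 7 contain three. The stated figure is not reproduced.

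**Step 2: subjects who stop earlier.** Any three successive gaps sum to 7, so the third visit is at +7 whichever session was dosed last.

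| Last dose at | Next three visits | Visits within +6 | Visits within +7 |
|---|---|---|---|
| First session of the week | +2, +4, +7 | 2 | 3 |
| Second session | +2, +5, +7 | 2 | 3 |
| Third session | +3, +5, +7 | 2 | 3 |

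**Step 3: readings that do give three.**

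- Count the dosing visit itself: offsets 0, 3 and 5 (Days 82, 85 and 87). Day 82 is before the Discontinuation Period, where SAP 9.2 says the events must occur.
- Count from DP Day 1: DP Days 1 to 6 are study Days 85 to 90 and contain Days 85, 87 and 89. This agrees with the Day 6 cut in SAP 10.5, but SAP 9.2 counts from the last dose.

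**Step 4: where the cut falls.** With the dosing day as day 0, 6 days end on 82 + 6 = Day 88. With the dosing day as day 1, they end on Day 87. From DP Day 1 they end on Day 90. The first two hold two visits after the dose; the third holds three.

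**Step 5: irregular schedules.** The documents allow an extra dialysis session with a dose (Protocol 6.4.1) and anticipate missed ones (Protocol 6.4.6).

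- Last dose Day 82, extra session Day 84: visits at +2, +3, +5.
- Last dose at an extra session on Day 83: +2, +4, +6.
- Day 82 missed, so last dose Day 80: +5, +7, +9.
- Day 85 missed: +5, +7, +10.

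The third visit can therefore come before or after day 7, and the two-visit count is a statement about the regular schedule.

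**Step 6: what is left out.** The screen works on when events occur, and Protocol 6.5.4.1 gives each event its own start date and time. With the dosing day as day 0, an event reported at the Day 89 visit with onset by Day 88 counts. One with onset on Day 89 does not.

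**The case against.** The best defence is that this is a wording slip with little effect. Visits are occasions for reporting, not the unit that the screen counts, so it would be wrong to infer that a third of the information is lost or that everything found at the Day 89 visit is missed. That stands: going from 6 to 7 days adds one onset day. All treatment-emergent events of the Discontinuation Period are still tabulated by preferred term for both discontinuation populations and listed, and the two withdrawal scales are analysed separately.

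It can also be said that the authors may have meant DP Days 1 to 6, in which case only the anchor is misstated. SAP 8.2.4.3 notes that the last dose of a week is not cleared until the next week's first dialysis, which fits that reading. It is plausible, but SAP 9.2 names the last dose as the anchor, and a programmer following it would stop at Day 88 rather than Day 90.

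A reader might go further. Onsets inside both the window and the Discontinuation Period run only from Day 85 to Day 88 for a completer, and one could infer that the SAP has cut short a two-week screen promised in the protocol. The documents do not support that. Protocol 8.9.4 describes a blinded review over two weeks but contains no three-event screen. SAP Section 12 declares analyses to identify possible withdrawal cases as an addition, and the SAP takes primacy. The screen also rests on published criteria that are not reproduced in full, so whether an early window is too narrow cannot be judged here.

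**Conclusion.** The inconsistency is real and limited. For any subject on the uninterrupted schedule, the 6 days after the last double-blind dose hold two dialysis visits and not three. For a completer, onsets on Day 89, the third visit day, fall outside a screen described as covering three visits. The gap is one onset day if the window is meant to run from the last dose, or two (Days 89 and 90) if DP Days 1 to 6 were meant. The documents do not say which was intended.

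This rests on regular sessions and on counting the dosing day as day 0. It does not hold for every subject, because extra or missed sessions shift the visits. The documents give no event rates, so the number of subjects affected cannot be estimated. Only the preselection for blinded review and the resulting flagged summary are touched; no efficacy result or hypothesis test is.

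**What to change.** In SAP 9.2, state the anchor (last dose or DP Day 1) and how days are counted, and make the window match the three visits. Either of these does so on the regular schedule:

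- 7 days from the last dose, with the dosing day as day 0 (through Day 89 for completers); or
- DP Days 1 to 6 (Days 85 to 90 for completers), in line with the Day 6 cut in SAP 10.5. If DP Day 1 is the first dialysis after the last dose, this also holds three visits for early stoppers: it ends at 2 + 5 = +7 or 3 + 5 = +8, and the third visit is at +7.

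Qualify the visit count as applying to the regular schedule, since neither window guarantees three visits after a missed session. Running the same screen over the full two weeks is an optional extra and not a correction.

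The cost is one sentence in the SAP and one changed limit in the program, to be settled before unblinding, plus a few more cases for blinded review.

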6.1.1.4 Double-blind Discontinuation Period

The Double-blind Treatment Period will be followed by a 2-week Discontinuation Period, during which no study drug will be administered and patients will be monitored for potential physical dependence, as follows:

- Daily patient completion of the Short Opiate Withdrawal Scale (ShOWS-Gossop 1990) (paper worksheet to be filled by each patient at home on nondialysis days and at the dialysis unit on dialysis days at similar time of the day for a given patient) (see worksheet in Appendix 6, Section 14.6)
- Completion of an Objective Opiate Withdrawal Scale (OOWS) worksheet (Handelsman 1987) by a trained observer at each dialysis visit (ie, 3 times a week) (see worksheet in Appendix 7, Section 14.7) (training of observer will be recorded)
- Recording of adverse events, medication used, body temperature, and vital signs at each dialysis visit.

Measurements will be taken starting at the end of the Treatment Period (Day 85) and then at each dialysis visit for up to 2 weeks following study drug discontinuation until Day 98 (Table 2).

During this Discontinuation Period, at each dialysis visit, patients will be asked to continue to report their daily Worst Itching Intensity NRS score over the previous 24 hours. In order to minimize bias, the OOWS and ShOWS will be introduced to the patients as health-assessment scales.

On the day of a dialysis visit, the OOWS and the ShOWS will be completed during the first hour (+1-hour window allowed) of dialysis so that dialysis-associated patient fatigue should minimally interfere with the completion of the scales. Double-blind study drug treatment assignment will remain blinded throughout the course of the Discontinuation Period. For patients who withdraw from the Double-blind Treatment Period early, every attempt will be made to conduct the 2-week Discontinuation Period.

A Structured Safety Evaluation will be performed weekly (preferably on Wednesday/Thursday) during the Discontinuation Period. The Structured Safety Evaluation is performed by study staff using a list of specific signs/symptoms (eg, mental status change, falls, gait disturbance).

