6.5.4.1 Adverse Events

Definition of Adverse Events

An adverse event is any untoward medical occurrence in a patient or clinical investigational patient administered a medicinal product and which does not necessarily have to have a causal relationship with this treatment. An adverse event can therefore be any unfavorable and unintended sign (including an abnormal laboratory finding, for example), symptom, or disease temporally associated with the use of a medicinal product, whether or not considered related to the medicinal product.

In this study, adverse events will be captured from the time a patient signs the ICF to the Follow-up Visit and include the following:

- Any new sign, symptom, or disease;
- Any new clinically significant or symptomatic laboratory/diagnostic test abnormality;
- Any clinically significant worsening of laboratory/diagnostic test abnormality;

- Any worsening (ie, clinically significant change in frequency, nature, and/or intensity) of a pre-existing condition.

A pre-existing condition is a condition that is present prior to signing the ICF for the study. Pre-existing conditions, such as illnesses, symptoms, reactions, progression of disease states, and other comorbidities, as well as laboratory/diagnostic test abnormalities, will be documented in the patient's record as medical history.

Signs and symptoms will be reported individually as adverse events (non-serious), unless a medical diagnosis was provided. Medical diagnosis, whenever provided, will be reported rather than individual signs and symptoms.

Any adverse event that satisfies any of the seriousness criteria described below will be reported as an SAE using the SAE Report Form, in addition to documenting in the eCRF. Serious adverse events that occurred up to 30 days after the last dose of study drug need to be documented on an SAE Report Form if they are deemed by the Investigator to be "Related" to study drug.

Adverse Event Severity Assessment

The Investigator will assess the severity (ie, intensity) of each adverse event (serious and non-serious) reported during the study based on his/her clinical judgment. The severity of each adverse event will be assigned to one of the following categories:

- Mild:** Transient, requires no special treatment, is easily tolerated by the patient, causes minimal discomfort, and does not interfere with the patient's daily activities

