- For the 5-D Itch Scale and the Skindex-10 Scale, the protocol specifies an MMRM analysis only. The SAP expands the analysis of these endpoints to include ANCOVA models with MI as the main analysis of these secondary variables, per Food and Drug Administration guidance. The MMRM model will be included as a sensitivity analysis.
- Analyses to identify possible cases of withdrawal from AEs added.

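### The SAP 9.2 withdrawal screen cannot select a withdrawal syndrome recorded as a single diagnosis, so such a case is missing from the dedicated withdrawal table

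*SAP*

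**What the plan says.** Three provisions matter.

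- **The screen (SAP 9.2).** The threshold and the window come first: "First, subjects that have 3 or more AEs occurring within 6 days (which will include 3 dialysis visits) of the last dose". Selection is then made by program against a closed list: "double-blind study drug from the list below programmatically will be selected for review". The list has nine items: dysphoric mood; nausea and/or vomiting; muscle aches; lacrimation and/or rhinorrhea; pupillary dilation, piloerection and/or sweating; diarrhea; yawning; fever; insomnia. Only those who pass go further: "The data for patients that have AEs potentially related to withdrawal (based on the above criteria) will be reviewed in a blinded fashion". Cases judged possibly related to withdrawal are then flagged and summarised. SAP 12 describes the addition in the same terms: "Analyses to identify possible cases of withdrawal from AEs added".
- **How events are recorded (Protocol 6.5.4.1).** The default is stated as: "Signs and symptoms will be reported individually as adverse events (non-serious), unless a medical diagnosis was provided". The exception is then made general: "Medical diagnosis, whenever provided, will be reported rather than individual signs and symptoms".
- **The protocol's intention (Protocol 8.9.4).** "Adverse events (AEs) and vital signs potentially related to withdrawal that occur during the 2-week Discontinuation Period will be identified" by blinded review of the data. The protocol sets no three-event threshold before that review.

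Separately, Protocol 6.1.1.4 provides for "Daily patient completion of the Short Opiate Withdrawal Scale" (ShOWS) and for an observer-rated scale (OOWS) at each dialysis visit. SAP 10.5 analyses both.

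**The concern.** The recording rule and the screening rule pull in opposite directions. The screen works by counting component symptoms. The recording rule removes component symptoms from the database once the investigator names the syndrome. A patient whose illness was clear enough to be diagnosed can therefore fail a screen that the same patient would pass undiagnosed.

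Protocol 7.1 says the Discontinuation Period was designed to assess potential physical dependence. The table of events potentially related to withdrawal is the display dedicated to reviewed cases. If it is empty or short, readers may take that as evidence on dependence without seeing that a diagnosed case could not enter it on the strength of the diagnosis.

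**Working it through.** The plan gives no figure to reproduce, and no sample size, power or alpha depends on this rule. The check applies the rule as written to hypothetical patients, then asks whether a capture rate can be derived.

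**1. Rule applied literally.** Inputs are the threshold of three, the nine-item list and the six-day window (SAP 9.2), and the replacement of symptoms by a diagnosis (Protocol 6.5.4.1). All events are taken to fall inside the window. The SAP does not say whether three or more counts event records or distinct list items, so both readings were tried.

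| Events recorded | Three records | Three distinct items |
|---|---|---|
| Withdrawal diagnosis only | not selected | not selected |
| Same illness as nausea, muscle aches, yawning, insomnia | selected | selected |
| Diagnosis plus 2 listed events | not selected | not selected |
| Diagnosis plus 3 listed events | selected | selected |
| Nausea, vomiting, diarrhea | selected | not selected |

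The first two rows are the finding: one illness, two outcomes, decided by how the site recorded it. In the fourth row the three listed events do the selecting and the diagnosis contributes nothing. The last row shows that the counting unit is undefined, but the result for a diagnosis is the same on either reading.

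**2. Is there a second route?** SAP 9.2 limits the review to subjects who meet its criteria. The custom query categories (SAP 16.2) and the events of special interest (SAP 16.3) have no withdrawal category; the only withdrawal term there is a convulsion term under seizures. SAP 10.5 does not link scale scores to selection. No second route is stated.

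**3. What still shows a diagnosed case?** SAP 9.2 tabulates Discontinuation Period events by system organ class and preferred term for both discontinuation populations, and lists all adverse events. A withdrawal diagnosis with onset in that period appears in both. What it loses is the review, the flag and the place in the withdrawal table.

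**4. Can a capture rate be derived for undiagnosed withdrawal?** Assume five listed symptoms, each entered as an event independently with probability r. Then

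P(selected) = 10r³(1−r)² + 5r⁴(1−r) + r⁵.

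- r = 0.1: 0.0081 + 0.00045 + 0.00001 = 0.0086, or 0.9%
- r = 0.9: 0.0729 + 0.3281 + 0.5905 = 0.991, or 99%

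| r | 10% | 20% | 30% | 40% | 60% | 70% | 80% | 90% |
|---|---|---|---|---|---|---|---|---|
| P(selected) | 0.9% | 5.8% | 16% | 32% | 68% | 84% | 94% | 99% |

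The number of symptoms, their independence and r are all assumptions; the documents supply none of them. The answer covers nearly the whole range, so no capture rate follows.

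**The case against.** The strongest reply is that little is lost. A diagnosed case remains visible in the preferred-term table and the listing, so an empty withdrawal table would sit beside a table that shows the diagnosis. The withdrawal table is descriptive, with no tests. Identifying cases from adverse events is the declared plan (SAP 12), and the nine items are attributed to published criteria that are not in the documents and are not judged here. All of this stands. It limits the size of the defect but does not remove it, because the screen still drops the diagnosed case.

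Three stronger readings are tempting and are not supported.

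- **A reader might infer that the withdrawal scales go unused.** That is true only of this screen. SAP 10.5 summarises ShOWS and OOWS, compares groups by analysis of covariance, and counts subjects by OOWS score, including each subject's maximum over the Discontinuation Period.
- **A reader might infer that this table is the only patient-level evidence on dependence.** The OOWS counts are patient-level too, although they are score tabulations and not reviewed cases.
- **A reader might infer that the screen would find almost no cases even if CR845 caused withdrawal.** That needs low recording probabilities. Protocol 6.5.4.1 requires observed, elicited and volunteered symptoms to be recorded as adverse events, and Protocol 6.1.1.4 has events recorded at each dialysis visit in this period. This text may well cover signs seen or elicited through the worksheets, although no explicit step carries a worksheet entry to the event page.

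**Conclusion.** The concern holds in a limited form. A withdrawal syndrome recorded as a single diagnosis cannot be selected by SAP 9.2. It is absent from the dedicated withdrawal table unless three listed events were also recorded separately in the window. This follows from the two rules read together and rests on no assumed rate; it assumes only that sites follow the recording rule and that the programmed screen is applied as written.

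The effect is confined to that table and the blinded review behind it. No efficacy endpoint, error rate or sample size is touched. How often the screen would miss withdrawal recorded as symptoms cannot be settled from the documents. The change is worth making because a stated rule gives a wrong result on a safety question that the Discontinuation Period was designed to address.

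**What to change.** In SAP 9.2, add a second, stand-alone selection criterion: any subject with an adverse event in the Discontinuation Period that codes to a withdrawal term (for example, drug withdrawal syndrome) also goes to blinded review, whatever the number of other events. Name the qualifying preferred terms in the SAP before unblinding. Leave the three-event criterion, the blinded review and the reporting populations as they are, and record the addition in SAP 12.

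The cost is a sentence or two of SAP text, a short term list, minor programming on data already collected, and a few extra blinded profiles. While the section is open, it would help to state whether the three-event criterion counts records or distinct list items.

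Using ShOWS, OOWS or temperature records as a further trigger is optional and not part of the required change. It would need its own window, a baseline rule (the Day 85 baseline falls three days after a last dose on Day 82) and an estimate of the added review load, none of which the documents provide.
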